5.2.3 Protections against psychological or mental discomfort

All interviewers will be trained to recognize signs of discomfort, distress, or anxiety. Interviewers will carefully monitor the participant's response, which will allow the interviews to be completed with minimum discomfort. Participants will take breaks when necessary to help alleviate any discomfort. Participants will also be reminded that they can refuse to answer any question that makes them uncomfortable and may take breaks whenever they are needed. They will also be informed that they have the right to decline participation in the study, or to withdraw consent at any time without adverse consequences. At the end of the interview, participants will be offered referrals to local mental health and substance use services. We have a network of referral resources in Khayelitsha, established through previous studies in this area.

There is a study protocol for managing distressed participants that all study staff will receive training in as well as regular supervision and debriefing. This protocol was developed by [name] and has been used across multiple studies with highly vulnerable populations, including traumatized women who use substances, people living with HIV, depression and problem alcohol use, and adolescents with alcohol and depression. In all her studies, [name] has successfully managed all incident cases of distressed participants and there have been no serious adverse or adverse events related to mental health or substance use harms. For participants who are distressed and at risk of harm, we will actively refer and link them to appropriate resources to help them cope with and deal with their distress. [name] is a registered clinical psychologist ([name]) and given the size of this study, will be able to provide active and daily clinical oversight to determine the level of care needed for each distressed participant. Our strategies to actively link distressed participants to care include debriefing with the participant. Our study team includes registered psychological counsellors who are trained and have the correct competencies to do this debriefing and [name] will be available to provide supervision and guidance. Strategies will include making (and fast-tracking appointments) at the appropriate agency and accompanying the distressed participant to the agency for their appointment to ensure that they receive the recommended services. [name] has worked in the target communities for more than 15 years and has an established network of mental health and substance use providers to whom we can refer participants should the need arise. Again, it is important to note that our patient participants are unlikely to require medical management of depression.

For both distressed participants and other participants with known difficulties relating to possible depression and substance use, we will provide individuals with active referrals to mental health and substance use (or other health services) on request. Active referral involves a discussion with the individual about the benefits of additional services, obtaining the participant's consent for release of information, identifying a suitable service to which the individual can be referred, allowing the individual to use a telephone to contact the service (or contacting the service on the individual's behalf) to make an appointment, writing a formal referral letter and providing this to the individual, and in some instances, transporting the individual to the service for their first appointment. As part of managing this process, we follow up with participants to see whether they were able to access the service, and if there were barriers to help them address these. We also follow up to assess whether there has been any improvement to their mental health status.

5.2.3 Health and Safety: COVID-19

To reduce the likelihood of COVID-19 transmission, the following precautions will be taken.

Vaccines. First, all study staff who are eligible to receive the COVID-19 vaccine will be encouraged to do so. All of our research staff currently working on this project are vaccinated and have agreed to share their vaccination status in this protocol.

Telephonic Interviews. To reduce contact with study participants, if possible, assessments with patient participants be conducted telephonically. Depending on the status of COVID-19, ongoing supervision and parts of the training may be held in-person or telephonically/over video.

In-Person Procedures. All staff members will be trained in COVID-19 safety protocols and the SAMRC standard operation procedures for the conduct of research during COVID-19. Staff members will have access to personal protective equipment (PPE) which will include sanitiser, masks, gloves, and face shield and Perspex dividers. Social distancing between staff member and the participant will be practiced, and all surfaces used will be disinfected before and after any interviews are held.

Assessments with patients will be conducted at the patient's home or over the phone. Assessments with CHWs will be conducted over the phone, at the location or the training, or where CHWs already work, so transportation should not be an issue for participation in assessments. However, we are aware that transport may be an issue for CHWs attending the training. If CHWs need to utilize public transport for the training, we will make sure that they feel safe to travel using this method, that it is their usual mode of transport for daily activities, and we will advise them to use masks while on public transport.

5.3 Potential Benefits of Proposed Research to Human Subjects

5.3.1 Participants

It is possible that participants will not directly benefit from this study. However, CHWs may find that they benefit from the additional information and skills that they learn in the training. Their patients also may benefit from them utilizing these new skills. CHW (in the initial and stepped-wedge trial), and patient participants (in the initial training), may also enjoy the opportunity to share their feedback on the CHW training.

5.3.2 Importance of the Knowledge to be Gained

From a broader perspective, the current study will likely have important implications for identifying how to optimally adapt and implement this CHW training program to promote re-engagement in care for patients co-infected with HIV and TB.

Initial Pilot Training

Findings from this formative study will inform the next iteration of this CHW training program, that we will implement in several clinics. We will seek approval for this next phase of the research in a separate submission.

Stepped Wedge Trial

CHWs are employed at every community health centre in South Africa, either through NGOs or the Department of Health. If this training program proves successful in reducing CHW stigma towards depression and substance use and promoting patient re-engagement in TB/HIV Care, it offers the potential for scale-

up. This research will also allow us to further understand barriers and facilitators to such scale-up.

6. Data Management

5.2 Data Storage

6.1.1 Data Acquisition and Transmission

Data collection occurs in South Africa at the specified data collection sites. All quantitative data will be entered into an electronic REDCap database (described below). All participants will be given a study ID. Personal identifying information of study participants will be kept entirely separate from their coded data.

Data Integrity. All interviews, measures, and observation notes will be conducted by a trained member of the study staff who will be supervised throughout the study.

Recordings. With the permission patients, some CHW sessions will be audio recorded for analysis. Please note that because CHWs—not patients—are the focus of these recordings, patients will not be enrolled in the study if their session is audio recorded. They will only be enrolled in the study if they choose to participate in a brief assessment about themselves and their CHW's visit. Roleplays with CHWs and either another CHW or staff member will be videorecorded. Qualitative interviews will be audio-recorded. If a roleplay, interview, or session is translated (e.g., because it is conducted in a non-English language), the translator will be a member of the study team and will leave out any potentially identifying data (e.g., names, locations). Roleplays will be recorded at the time of the training and saved in a secure location that only study-staff can access (i.e., UMD Box) and saved with the CHW's study ID. Qualitative interview recordings will also be stored in a secure location that only study-staff can access (i.e., UMD Box) and saved with the participant's study ID. CHWs will receive verbal consent from their patients before recording a normal session. If the patient does not want their session recorded, the visit will continue as usual. During training and supervision we will stress to CHWs that it is okay if none of their patients want to be recorded. If a session is recorded, the CHW will be asked to let the study team know. The study team will pick up the recording device as soon as possible and upload it to a secure database using the study computer. The audio file will then be deleted from the digital recorder. Computer audio files will be saved in a secure location that only study-staff can access (i.e., UMD Box) and saved with the CHW's study ID. Following the South African good clinical practice (GCP) guidelines and guidelines set by the American Psychological Association (APA; APA Record Keeping Guidelines, Guideline #7), recordings will be maintained until seven years after the publication of the study.). The ethics committee will review study procedures at least annually to review procedures pertaining to participant confidentiality.

Identifiable Data. Consent forms and any other documents with identifiable information will be kept in a separate, secure filing cabinet at the secure SAMRC study site.

De-Identified Data. De-identified data will be kept in a secure electronic system, such as Box through UMD. Only authorized study staff will have access to this data.

Link. The link between the names and ID numbers of participants will be kept separate from all other data on a secure server at SAMRC and in a password protected document. The link will be destroyed after data analysis for the study has ended. Only trained study staff in South Africa will have access to this link.

6.1.2 Data Entry Methods

Fidelity Analysis. Roleplays and sessions with patients and roleplays will be analysed for fidelity. If done in English, team members will review the recording in English on UMD box. If not done in English, study team members who speak isiXhosa will review the recording in isiXhosa on UMD box and complete the rating using an isiXhosa version of the measure.

Quantitative Assessments. Data entry will occur as close to real time as possible to facilitate data management and monitoring of study operations. If assessments are done on paper, they will be scanned by a research assistant as soon as possible and sent to the study's secure server. The paper assessment will then be filed away at a secure location at the MRC and the scanned assessment will be entered on REDCap.

REDCap. Demographic and measure data will utilize REDCap through UMD, a secure software toolset and workflow methodology for electronic collection and management of research and clinical trial data in real-time. SAMRC also uses REDCap for data collection. REDCap provides a web-based application with an intuitive interface for users to enter data and have real time validation rules (with automated data type and range checks) at the time of entry. REDCap data collection projects data on a thorough study-specific data dictionary defined in an iterative self-documenting process by all members of the research team with planning assistance from UMD. All information entered on REDCap will be de-identified in order to protect participants' identities.

6.1.3 Quality Assurance

Data Completeness. To ensure the usability of self-report data, a member of the research team will review all self-report measures to ensure their completeness. Using an electronic data capture system such as REDCap is meant to reduce errors in the data entry and management process. Using REDCap, missing data can be reduced by making items required to answer before moving on to the next item and effort and error associated with data entry can be reduced because there is no manual entering of data at a later timepoint by research assistants.

Confidentiality. Data from all participants will be identified on study materials (including electronic study materials saved on a secure study drive such as Box) will be identified only by participant number and date of visit. By recording the study data in this manner, the information can be considered 'de-identified.'

5.3 Data Safety and Monitoring Plan

6.2.1 Regulatory Issues

The procedures laid out in this document will be followed, in compliance with NIH requirements as well as South African good clinical practice guidelines, to ensure the safety of study participants and the validity and integrity of data.

Before initiation of this study, the protocol, informed consent, and all other materials used with participants in this study will be reviewed and approved by SAMRC ethics committee. The study team will additionally submit a report to SAMRC ethics committee on an annual basis.

6.2.2 Amendments

Any changes to the protocol or amendments will be submitted to the SAMRC ethics committee before they are implemented.

6.2.3 Reporting Definitions

Unanticipated problems are any incidents/ experiences/ outcomes that are (1) unexpected (in terms of nature, severity, or frequency), (2) related or possibly related to participation in the research, AND (3) suggest that the research places subjects or others at a greater risk of harm (including physical, psychological, economic, or social harm) than was previously recognized.

Adverse events (AEs) are any untoward or unfavourable medical occurrences in a human subject, including any abnormal sign, symptom, or disease, temporally associated with the subject's participation in the research, whether or not considered related to the subject's participation in the research.

Serious adverse events (SAEs) are any adverse events that meet any of the following criteria: (1) results in death; (2) is life-threatening; (3) requires inpatient hospitalization or prolongation of existing hospitalization; (4) results in a persistent or significant disability/ incapacity; (5) results in a congenital anomaly/ birth defect; OR (6) may jeopardize the subject's health and may require medical or surgical intervention to prevent one of the other outcomes listed in this definition.

Labelling of AEs and SAEs.

Severity. AEs and SAEs will be labelled according to severity by one or both of the PIs, based on their impact on the patient. An AE will be termed “mild” if it does not have a major impact on the patient, “moderate” if it causes the patient some minor inconvenience, and “severe” if it causes a substantial disruption to the patient’s well-being.

Likelihood. AEs will also be categorized according to the likelihood that they are related to participating in the study. Specifically, they will be labelled “definitely unrelated”, “possibly related”, “probably related”, or “definitely related”.

6.2.4 Protocol violations

Study staff will inform the Principal Investigators (PI) as soon as they are aware of any violations to the protocol. The South African PI will report any violations and the corrective actions taken to prevent further violations within 7 days to the SAMRC ethics committee.

6.2.5 Adverse events and unanticipated problems

As this study consists of low-risk one-time visits, we do not anticipate having any AEs, SAEs, or unanticipated problems. However, the plan for monitoring and reporting AEs, SAEs, and unanticipated problems is below.

Monitoring. Participants in semi-structured interviews will be monitored for AEs, SAEs, and unanticipated problems during the one-time interview session.

Reporting to SAMRC HREC.

AEs. If any AEs occur, they will be reported to the SAMRC HREC during the yearly progress report.

SAEs. All SAEs will be reported to SAMRC HREC within 48 hours of the team discovering the SAE, regardless of whether or not the SAE is related.

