3.2.2 Stepped-Wedge Trial

We will use a stepped-wedge design.

CHWs will be clustered based on the site at which they work. When recruiting participants, we will aim to recruit approximately 20 CHWs per cluster.

CHWs across all clusters will be recruited and complete a baseline assessment at approximately the same time. In stepped-wedge trials, all groups have different intervals of a baseline period in which they are not exposed to an intervention (which we refer to as “treatment as usual” or “TAU”). Following this, at measurable intervals (steps), one group at a time will receive the training intervention. This process continues until all clusters have received the intervention. Then, at least one more follow-up assessment occurs after all clusters have received the intervention.

In this study, when a cluster receives the intervention (versus continues TAU) depends on whether they are randomized to Training Time #1, Training Time #2, or Training Time #3. Each training time will occur at a measurable intervention (compared to when the baseline assessment was conducted) so that the doses of TAU are discernable.

During data analysis, outcome variables will be compared between people before taking the intervention (TAU only; timepoints are baseline assessment (t1) and pre-training assessment (t2)) and with the same group of people after the intervention (TAU+Training; additional timepoints are 3-month follow-up (t3) and 6-month follow-up (t4) after adjusting for individual random effect and time effect.

Randomization will not affect any other TB/HIV-related clinic services or mental health training.

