3.3.1 Stepped-Wedge Trial

3.3.2a CHW Participants

Participants will be 60 CHWs who are employed by one of the NGOs listed above. Please see Section 3.1.2 (above) for more information on these NGOs.

Rationale for enrolment numbers.

The number of CHWs to enroll ($N=60$) was determined through power calculations based on the primary effectiveness outcome (i.e., CHW stigma measured with the SDS).^{20,43,44}

A linear mixed model will be used for the primary outcome, considering both the within clinic correlation (i.e., multiple CHWs working at the same clinic) and the within person correlation (i.e., repeated measures on CHW stigma over time). In the power analysis, anticipated standardized effect sizes were defined from (1) a meta-analysis of 13 randomized clinical trials of mental health stigma reduction interventions that shows a standardized effect size of 0.63 on measures of stigma [121], and (2) prior work in sub-Saharan Africa using the SDS to test changes in mental health stigma among community mental health volunteers that had an effect size of 0.75.⁴⁴ Assuming similar baseline characteristics from a prior study using SDS among community health workers,⁴⁴ and an intra-class correlation of 0.1 within clinic and 0.3 within person, with 60 CHWs, our study can achieve a power of 86% at a significance level of 0.05 and a CHW training effect of 0.63, and 96% power at a training effect of 0.75.

A subset of these CHWs (up to $n=20$) will then participate in qualitative interviews. We will select CHWs for these further interviews by classifying CHWs based on level of change in stigma during the training. We intend to include CHWs who had reduced stigma following the training, no change in stigma following the training, and increased stigma following the training. We will also ensure that recruited CHWs represent the multiple NGOs that participated in the training. Only CHWs who attended the training will be eligible. We anticipate that this number of participants will allow us to reach theoretical saturation for qualitative analysis.⁴⁷

Eligibility.

To be eligible, CHWs must meet all of the criteria in the below table.

CHW Eligibility Criteria

Inclusion	Exclusion
1. At least 18 years old	1. Unable to complete informed consent or study procedures in English or isiXhosa
2. Be employed as a CHW through a partner NGO that provides HIV/TB CHW services	2. Unable to complete training in English

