3.5.2 Stepped Wedge Trial

3.5.2a CHW Screening & Consent

Potentially eligible CHWs—referred to us by NGO staff will be screened for eligibility. If eligible and interested in participating, they will undergo informed consent procedures. As part of this process, participants will be informed of all the potential risks and benefits to taking part in the study. Participants will be reminded that participation is voluntary, that they can decline to answer any questions they are not comfortable answering, they can leave the study at any point, and their decision to participate in the study will not impact their job. As part of signing the consent form, they will also consent to the Protection of Personal Information Act 4 of 2013.

3.5.2b CHW Baseline and Pre-Training Assessments

Baseline Assessment. Upon giving willing, informed consent, CHWs will complete a baseline assessment with study staff. The baseline assessment will consist of self-report questions around CHWs' demographic characteristics and job, personal mental health questions, questions around knowledge of HIV, TB, depression and substance use, and questions around stigma.

Pre-Treatment Assessment. Immediately before their training, participants will complete a pre-training assessment. At this visit, participants will be asked to answer the same self-report questionnaires and as they did at baseline (with the exception of demographic and job information, which will not be asked again). All CHWs will also complete a brief (~10 minutes) role-play vignette with a staff member who is minimally involved in delivering the training, which will be videotaped and later coded for stigma using the ENACT.

3.5.2c CHW Training

After the baseline assessment all groups will receive at least one dose of TAU. Based on the training time to which their cluster was randomized, CHWs will then be invited to participate in a training on mental health and substance use.

Clusters randomized to Training Time #1 will receive the training first (while the other training times continue to receive TAU), followed by Training Time #2 (while the final training time continues to receive TAU), and finally, Training Time #3.

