The training in the stepped-wedge trial will be the as the initial training, with minimal adaptations based on participant feedback (e.g., potentially an additional day, allocating more or less time to specific concepts, etc.). It will still be conducted in English, as all CHW trainings offered by the Western Cape Department of Health are required as part of the CHW certification occur in English. Roleplays will be conducted in English (training language) or isiXhosa (patients' language). Additionally, our training team consists of English, isiXhosa, and Afrikaans mother-tongue speakers; therefore, our team will be able to address questions and further explain concepts in these languages if needed.

3.5.2d CHW Post-Training Assessments

In addition to the Baseline and Pre-Treatment Assessments (which both occur before the training, and therefore, measure TAU), CHWs will also be required to complete two additional assessments after the training:

3-Month Follow-Up Assessment (3MFU): All participants will be invited to complete a follow-up assessment approximately 3-months after their training (3MFU). At this visit, participants will answer the same self-report questions they answered at the Pre-Training Assessment, answer additional questions about their perceived feasibility/acceptability of the training, and complete a roleplay for later ENACT coding.

6-Month Follow-Up Assessment (6MFU): All participants will also be invited to complete another follow-up assessment approximately 6-months after their training (6MFU). At this visit, participants will answer the same self-report questions they answered at the 3MFU and complete a roleplay for later ENACT coding. A subset of CHWs will also participate in semi-structured individual interviews in which they answer open-ended questions about their perceived feasibility/acceptability of the training.

3.5.2e Additional CHW Self-Report Measures

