1.2 Steps to follow with very distressed participants

There may be instances where participants are so distressed that you are concerned for their safety and may not be able to continue with the appointment. Remember that we have made it clear in the consent form that there are exceptions to our promise of confidentiality. If participants express the intent to harm themselves or others, or ongoing abuse and/or neglect of children, then we have a duty to report this matter to the proper authorities, e.g. the police, courts or social workers. Field staff will provide information on toll-free hotlines that people can call to talk to someone and seek assistance, as well as local resource information.

If during the course of the study you are concerned that a participant intends to harm him/herself or others, then mandatory reporting procedures need to be followed on completion of the appointment. Immediately inform the project manager and the principal investigator (PI) who will report the incident to the various ethics committees and our project officer within 72 hours.

In these instances, please follow the following steps:

- As far as possible, complete the study appointment
- Indicate to the person that they seem upset or anxious
- Remind the person of the limits of confidentiality as expressed in the consent form, and your duty to report
- Follow the mandatory reporting procedures described below
- Complete the referral and release form
- Call the agency to make an immediate appointment
- Provide the patients with a copy of the referral letter in an envelope and keep one in the participants folder
- Provide the patient with a copy of the resource guide for additional services
- At the end of the appointment, document this referral in the Participant's file
- Complete an incident report form and immediately send to the project manager and PI who will both keep copies on file and will report the incident to the relevant regulatory bodies.

2. Mandatory reporting procedures

It is possible that a participant will indicate during the course of a discussion that s/he is in immediate danger of harm or poses a threat to the safety of others. We want you to feel that you can handle this situation with confidence.

There are essentially three situations in which there may be immediate danger of harm:

- 1) **Suicidal Intent:** The participant expresses a desire to hurt or kill themselves.

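### The only adverse-event monitoring rule (Section 6.2.5) is written for one-off interviews and does not fit a trial in which each CHW has four assessments plus training and supervision

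*Combined protocol and SAP*

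**What the plan says.** Section 6.2.5 opens with a premise about the whole study: "As this study consists of low-risk one-time visits, we do not anticipate having any AEs, SAEs, or unanticipated problems". Its one sentence on monitoring follows: "Participants in semi-structured interviews will be monitored for AEs, SAEs, and unanticipated problems during the one-time interview session". The same section then sets the reporting rules. Adverse events (AEs) go to the ethics committee in the yearly report, and every serious adverse event (SAE) goes within 48 hours of the team discovering it, related or not.

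The stepped-wedge schedule is different in kind:
- Section 3.3.2a: "Participants will be 60 CHWs who are employed by one of the NGOs listed above" (the table in Section 3.3 says approximately 60).
- Section 3.5.2b: a baseline and a pre-training assessment. The baseline includes "personal mental health questions", and the questionnaires other than demographics and job details are repeated later.
- Section 3.5.2d: "CHWs will also be required to complete two additional assessments after the training", at 3 and 6 months.
- Sections 3.5.2b, 3.5.2d and 3.5.2e: roleplays at pre-training, on the last training day, and at both follow-ups.
- Section 7: training and supervision for each of the three groups.

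The interviews named in the monitoring rule involve few CHWs and come late. Section 3.5.2d, under the 6-month follow-up, says: "A subset of CHWs will also participate in semi-structured individual interviews". Section 3.3.2a caps that subset at 20, and Section 3.3.2b caps stakeholders at 28.

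Appendix 2, section 1.2, has a separate route for participants thought likely to harm themselves or others. The project manager and principal investigator are told at once, and the latter is to "report the incident to the various ethics committees and our project officer within 72 hours".

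**The concern.** The monitoring rule fits a study in which each person is seen once for an interview. The stepped-wedge trial follows each CHW over several months, and the assessments that touch on personal mental health fall outside the rule. Section 5.1.2 itself recognises that CHWs may be uncomfortable talking about their own stigmatising behaviour.

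Section 6.2.3 defines an AE broadly, as an unfavourable medical occurrence linked in time to participation, whether or not participation caused it. Such events are found reliably only if participants are asked. Under Section 6.2.5 as written, nobody is instructed to ask at baseline, pre-training or either follow-up assessment. The AE summaries sent yearly to the ethics committee and to the funder would then rest on what staff happened to notice, except in the interviews. No efficacy analysis depends on this. What is at stake is how complete the safety record is, and whether a low count can be interpreted.

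**Working it through.** The plan states no figure on this point, so there is nothing to reproduce. The check counts planned contacts that fall under the monitoring rule.

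**Inputs**
- CHWs: 60 (Section 3.3.2a).
- Assessments per CHW: 2 before training and 2 after, so 4 (Sections 3.2.2, 3.5.2b and 3.5.2d).
- CHW interviews: at most 20 (Section 3.3.2a).
- Stakeholder interviews: at most 28 (Section 3.3.2b). The plan calls these qualitative. Counting them as semi-structured favours the plan.
- Supervision sessions in the stepped-wedge trial: number not stated. As an assumption, 4 per CHW, taken from the initial pilot's weekly sessions for about a month (Section 3.5.1g).

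**Step 1. CHWs reached.** 60 − 20 = 40, so at least 40 of 60 CHWs (67%) never come under the rule.

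**Step 2. Share of contacts covered.** Share = interviews / (interviews + other contacts), with 60 × 4 = 240 planned assessments.

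| Contacts counted | CHWs only | With stakeholder interviews |
|---|---|---|
| Assessments and interviews | 20 / (240 + 20) = 20/260 = 7.7% | 48 / (240 + 48) = 48/288 = 16.7% |
| Plus one training contact per CHW (60) | 20/320 = 6.3% | 48/348 = 13.8% |
| Plus 4 assumed supervision sessions per CHW (240) | 20/560 = 3.6% | 48/588 = 8.2% |

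**Step 3. Attrition.** The follow-up assessments are by invitation, so 240 is a planned number. As an extreme case, count only the two assessments before training, 60 × 2 = 120. The share is then 20/140 = 14.3% for CHWs, or 48/168 = 28.6% with stakeholders. The covered contacts remain a minority.

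**Step 4. Timing.** By the month labels in Section 7, baseline is month 3, the 6-month follow-up is months 12 to 14, and the interviews are months 13 to 15. Active monitoring of any CHW therefore starts about 9 to 12 months after baseline. Only CHWs who attended the training can be interviewed. The usual-care period, training, supervision and 3-month follow-up all pass before it starts.

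**Step 5. Does another section fill the gap?** Sections 6.2.3 and 6.2.6 define and route events. Section 5.2.3 and Appendix 2 deal with distress, suicidal intent, intent to harm others and child abuse. None tells staff to ask about AEs at the assessments. A hospital admission between visits, for example, would trigger none of the distress procedures.

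Section 6.2.5 also governs the initial pilot (25 CHWs with three assessments each, and up to 75 patient assessments). None of those contacts is described as a semi-structured interview. They are left out of the counts above.

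**The case against.** The strongest reply is that the text does not confine AE handling to interviews, and the word only does not appear in it. A reader might infer that events outside the interviews go unreported, or that a report of no AEs would mean merely that none arose in an interview. The documents do not support either reading. Section 6.2.5 requires any AE that occurs to be reported, and any SAE that the team discovers, at whatever contact. Section 6.2.3 applies to any participant, and Section 6.2.6 adds reporting to the funder. All study staff are trained in the distress protocol. Appendix 2 applies at any study appointment and requires an incident form for serious cases, which is documented capture of one class of event. This part of the reply stands: the assessments are not unobserved, and the percentages above count contacts, not events missed. The documents give no basis for estimating missed events.

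It is also fair that the protocol calls the study minimal risk (Section 5.1), and that formal AE questioning at every training day and supervision session would exceed what is needed to remove the inconsistency. That argues for a light remedy. It does not rescue a rule built on a description of the visits that the schedule contradicts.

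A reader might also see the 72 hours in Appendix 2 and the 48 hours in Section 6.2.5 as a plain contradiction. They have different triggers: an expressed intent to harm in one case, an SAE in the other. An expression of intent is not automatically an SAE under Section 6.2.3. The two overlap only when one incident is both.

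**Conclusion.** The point holds as a gap in active ascertainment. The single-visit premise of Section 6.2.5 conflicts with the schedule in Sections 3.2.2, 3.5.2 and 7, and the only rule on who is monitored and when reaches at most 20 of about 60 CHWs. On the planned schedule that is at most 7.7% of CHW assessments and interviews, or 16.7% with stakeholder interviews, and less once training and supervision are counted. The sizes rest on 60 CHWs, full attendance at four assessments, and interview numbers at their caps. The supervision rows also rest on the pilot's frequency. That most contacts fall outside the rule does not depend on any of these.

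The point does not extend to reporting duties or to the management of acute distress, both of which apply beyond the interviews. The two reporting clocks are a minor matter of clarification. The change is worth making because it is cheap and makes a low AE count easier to interpret. The primary analysis is unaffected.

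**What to change.** In Section 6.2.5:
1. Delete the statement that the study consists of one-time visits, and describe the repeated assessments.
2. Restate the monitoring sentence so that every enrolled participant is asked about AEs, SAEs and unanticipated problems at each scheduled assessment and each interview.
3. State that events noticed during training, supervision or roleplays are recorded on the same log, without requiring a formal enquiry at those contacts.
4. As a minor addition, state how the Appendix 2 and Section 6.2.5 reporting times are reconciled when an incident is also an SAE. Which time should govern is for the investigators and the ethics committee.

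Cost: a wording amendment submitted to the ethics committee, one added question on assessments already scheduled, and one shared log. No extra visits are needed.
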